### 1.2 Primary endpoint

The primary endpoint is time until cessation of oral shedding of SARS-CoV-2 virus, defined as the time in days from randomization to the first of two negative oropharyngeal tests. Patients who do not experience the endpoint will be censored at 28 days after randomization (end of study) or at the time of premature withdrawal.

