## 3 HANDLING OF MISSING AND CENSORED DATA

All efforts will be made to minimize instances of missing data. However, we expect some missing data will occur. Our analyses will assume data are missing at random. For the primary endpoint of time to shedding cessation, any participant who drops out prior to having two consecutive negative tests will be censored at their last positive test. Participants who have no post-randomization test results available or a single test result that is negative will be censored at day 1. Similarly, participants will be right censored for the time to symptom resolution or progression at the time when their last symptom questionnaire is completed. Participants who are asymptomatic at screening and never report symptoms thereafter will be considered to have met symptom resolution at study Day 1. For other missing data, we will use multiple imputation-based analyses. This approach will be applied to any analysis involving endpoints or key

variables where any missing data occurs in order to adhere to the ITT principle. Sensitivity to assumptions regarding missingness will be addressed through sensitivity analyses.

If more than 5% of participants do not have the time of shedding cessation observed (i.e. they are right-censored), we will perform a sensitivity analysis to evaluate the robustness of our findings to missing data assumptions. In the sensitivity analysis, among those missing timing of shedding cessation, we will assume varying proportions (e.g. 25%, 50%) of participants in each arm who would have ceased shedding by Day 28. The proportions will differ by arm so we can evaluate whether our findings stand if it were true that people who dropped out stopped shedding earlier in the placebo arm vs the active arm.

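### The SAP's missing-data sensitivity analysis is defined by right-censoring, so as written it also takes in completers still positive at Day 28, although its stated aim concerns dropouts

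*SAP*

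**What the plan says.** SAP section 1.2 creates two kinds of censored participant: "Patients who do not experience the endpoint will be censored at 28 days after randomization (end of study) or at the time of premature withdrawal".

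SAP section 3 sets the trigger without separating them. It counts everyone for whom the data "do not have the time of shedding cessation observed (i.e. they are right-censored"); once that count passes 5% of participants, a sensitivity analysis follows. The group to be reassigned is described this way: "among those missing timing of shedding cessation, we will assume varying proportions (e.g. 25%, 50%) of participants in each arm". For the chosen share, the assumption is that these are people "who would have ceased shedding by Day 28". On the split between arms it states: "The proportions will differ by arm". The closing sentence gives the purpose, which is to see whether the findings stand if participants who left the study had stopped shedding earlier on placebo than on active treatment.

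The protocol's statistical section has no matching sensitivity analysis, so nothing there settles which group is meant.

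**The concern.** A completer with a positive swab at Day 28 has a right-censored cessation time, but the question that this analysis asks about that person is already answered: shedding had not stopped by Day 28. Assuming otherwise is not a missing-data assumption, because it contradicts an observed result.

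If Lambda works, such participants are more numerous in the control arm. A scenario that favours control would therefore recode observed outcomes mostly in that arm and pull the hazard ratio toward 1. A positive result could look fragile to dropout when dropout was not the cause. The operational definition (all right-censored) and the stated purpose (dropouts) give materially different analyses, and the SAP leaves the choice to the analyst.

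**Working it through.** **Who falls in the set.**

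| Participant | Right-censored under SAP 1.2 | Status at Day 28 | Within the stated aim |
|---|---|---|---|
| Withdrew or lost before Day 28 | yes | unknown | yes |
| Completed, Day 28 swab positive | yes | known: still shedding | no |
| Completed, first negative at Day 28 | yes | negative, unconfirmed | not addressed |

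The SAP gives no expected number censored, so there is no figure of its own to reproduce. The threshold is 0.05 × 120 = 6, so 7 or more participants trigger the analysis.

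**Share positive at Day 28, from the SAP medians.** SAP 4.2 gives medians of 14 (control) and 7 days (treatment), with 60 per arm. An exponential shape is my assumption, and there is no dropout in this step.
- Control: 0.5^(28/14) = 0.25, and 60 × 0.25 = 15.
- Lambda: 0.5^(28/7) = 0.0625, and 60 × 0.0625 = 3.75.
- Total 18.75 of 120 (15.6%). The exact binomial calculation gives P(more than 6) = 0.9998.

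**All completers censored at Day 28.** The endpoint needs two consecutive negatives (Protocol 5.1) and the last visits are Days 14, 21 and 28 (Protocol 9.1.2), so the last confirmable first negative is at Day 21.
- Control: 0.5^(21/14) = 0.354, or 21.2 of 60. Lambda: 0.5^(21/7) = 0.125, or 7.5 of 60.
- Total 28.7 of 120 (24%). The difference, 28.7 − 18.75 ≈ 10, is negative at Day 28 without confirmation.

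**The same shares from mean 14, SD 4.** SAP 4.2 also gives this description. It is not the exponential above, whose mean and SD would both be 14/ln 2 = 20.2. Here I assume a normal shape and a treatment mean of 7 with SD 4.
- Positive at Day 28: control z = (28 − 14)/4 = 3.5, tail 0.00023, and 60 × 0.00023 = 0.014. Lambda is effectively nil.
- No confirmed endpoint: control z = (21 − 14)/4 = 1.75, tail 0.040, or 2.4 of 60. Lambda adds 0.014. The total is about 2.4 of 120.
- P(trigger) without dropout is about 1%. With 10% dropout in both arms it is about 87%, and with control-only dropout about 58%.

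**Effect on the hazard ratio.** Simulation with exponential times (medians 14/7), 60 per arm and 10% dropout in both arms, with 50% of control and 25% of Lambda in the pool reassigned as ceased. In the first two rows cessation is observed continuously, dropout is uniform over 28 days, and the Cox model contains arm only. Brackets give the share of trials with p < 0.05.

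| Times given to reassigned Day 28 positives | No reassignment | Dropouts only | Dropouts and Day 28 positives |
|---|---|---|---|
| Uniform over Days 21–28 | 2.02 (93%) | 1.91 (89%) | 1.73 (80%) |
| Uniform over Days 0–28 | 2.03 (94%) | 1.93 (91%) | 1.60 (66%) |
| Further variant, groups added one at a time | about 2.0 | 1.95 | 1.76 |

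Adding the unconfirmed Day 28 negatives in the last variant gives 1.69.

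**Size of the pool and trigger.** On the visit schedule, with exponential times and 10% dropout in both arms, the literal pool is about 33 of 120 and the trigger fires in essentially every trial. Limited to dropouts, the pool is about 7.4 of 120 and the trigger fires in about 61% of trials (about 13% if dropout is in control only).

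**The case against.** The strongest reply is that SAP section 3 already shows what is meant. The analysis is described as testing missing-data assumptions, the pool is worded as those lacking a cessation time rather than as those right-censored, the phrasing about Day 28 is counterfactual, and the last sentence speaks of people who dropped out. An analyst guided by that sentence would not recode a positive Day 28 swab. This stands as evidence of intent. A reader might infer that the plan definitely orders observed outcomes to be overwritten, and the documents do not support that. But the parenthesis defines the set, nothing excludes completers, and the same section names dropouts explicitly when it sets their censoring rule.

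A reader might also infer that the trigger always fires. That holds, almost surely, under exponential times with medians 14/7, but not under mean 14 and SD 4. Protocol 2.1.1 also points lower, with 22% shedding from the oropharynx 14 days after symptom onset. An exponential through that point gives 0.22² = 4.8% of control at Day 28 and, at a hazard ratio of 2, 0.22⁴ = 0.2% of Lambda, or about 60 × 0.048 + 60 × 0.002 ≈ 3 of 120. That clock starts at symptom onset rather than randomization, so it is only a rough guide.

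Nor are all completers censored at Day 28 known shedders: about 10 of the 29 are unconfirmed negatives, whose confirmed cessation is truly unobserved. Finally, firing the trigger only adds an analysis, the SAP calls for a range of proportions rather than one decisive scenario, and the distortion shown here runs toward the null.

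**Conclusion.** The definition and the purpose in SAP section 3 disagree, and the definition as written includes people whose Day 28 status is known. The consequence ranges from material to negligible with the assumed distribution. At one end, about 19 of 120 are positive at Day 28 (15 control, 4 Lambda), the trigger is near-certain, and the hazard ratio is about 1.7–1.8 (as low as 1.60 if reassigned times are spread over the whole 28 days) instead of about 1.9–1.95. At the other end, essentially nobody is positive and the zero-dropout trigger probability is about 1%. Between them, with exponential times and a hazard ratio of 2, the expected share positive at Day 28 falls below 5% once the control median is under about 8.1 days: 0.5^(28/8.12) = 0.092 in control, 0.092² = 0.008 in Lambda, average 0.05.

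These figures rest on assumptions outside the documents: the distribution shape, the treatment SD, uniform dropout times and the times given to reassigned participants. The 50%/25% split uses the SAP's own example proportions, but pairing them by arm is my choice.

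It would be wrong to infer that the main result is at risk. The primary Cox analysis, its test and the sample size do not depend on this rule. It should be corrected before the analysis is run, because two analysts could follow the text in good faith and report different robustness results.

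**What to change.** In SAP section 3:

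1. Replace the parenthesis that equates an unobserved cessation time with right-censoring by: *because they were censored before Day 28 through withdrawal, loss to follow-up or missing swabs*.
2. Use only this group for both the 5% trigger and the reassignment.
3. State that participants with a positive Day 28 swab stay censored at Day 28 in every scenario.
4. Give one rule for participants whose first negative is an unconfirmed Day 28 swab. For example, censor them at Day 28 in the main scenarios and add one scenario that counts them as ceased at Day 28.
5. State how cessation times are assigned to reassigned participants, since the result depends on it.

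The cost is a few SAP sentences. No new data are needed, and the primary analysis does not change.

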## 4 SAMPLE SIZE CONSIDERATIONS

### 4.1 Statistical hypothesis

For the primary comparison, the following will be tested:

- Null hypothesis: time to cessation of oral shedding is equal in control and treatment;
- Alternative hypothesis: time to cessation of oral shedding differs between control and treatment.

Hypothesis tests will be two sided and conducted at an overall alpha = 0.05 level of significance.

### 4.2 Determination of sample size

We assume that the mean duration of virologic shedding in individuals receiving standard of care is 14 days, with a standard deviation of 4 days.

Assuming 1:1 randomization and the use of a two-sided log rank test at the alpha=0.04999 level of significance for the final analysis, 79 events will provide 80% power to detect a hazard ratio of 2.03. This leaves alpha=0.00001 to check for overwhelming efficacy after 50% of participants have completed 24 hours of follow-up. Assuming the control and treatment arm median cessation of shedding is 14 and 7 days, respectively, a two-month accrual period, a two-week follow-up period after randomization of the last patient, and a drop out of 10% in the control arm, it is estimated that the total sample size required to achieve 79 events is 120 (60 patients in each arm).

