Statistical Analysis and Sample Size Considerations	We will evaluate the intention-to-treat (ITT) population, defined as the original treatment assignment groups after randomization, for the primary efficacy analysis. We will analyze the per-protocol group as supportive evidence for the primary efficacy analysis. Approximately 120 patients with COVID-19 infection are planned to be enrolled and randomized, and we conservatively assume that 90% of participants will complete follow-up. The primary endpoint will be assessed in all patients. We assume that the mean duration of virologic shedding is 14 days in individuals receiving placebo, with a standard deviation of 4 days (Zhou et al, Lancet 2020). With 60 patients randomized per arm, we will have 80% power to detect a minimum 50% reduction in virologic shedding in participants receiving Lambda.

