## **6 POTENTIAL LIMITATIONS AND MITIGATION STRATEGIES**

Given the fast-changing landscape during the COVID-19 pandemic, we provide the following power calculations showing how potential study alterations would impact the study's operating characteristics. Potential alterations considered are designed to mitigate the impact of newly identified therapies that change the standard of care and/or slower than planned enrollment.

The study team plans to evaluate the rate of enrollment two weeks after enrollment opens. If fewer than 10 patients have been enrolled within the first two weeks, a potential solution to increase enrollment is to change the randomization ratio to be 2:1 on treatment:control. We have selected a 1:1 ratio under the assumption of equipoise; however, we anticipate that participants may not want to have a 50% chance of being randomized to placebo. To address this concern, we could increase the ratio in order to reduce the chance of being randomized to placebo to 33%. Under the assumptions described above, the change in the randomization ratio will not require a larger sample size.

We also consider how a change in the standard of care could impact our study's power. If the standard of care changes and our expected effect size decreases, our expected power would decrease to 61%, 41%, or 22% under an assumed hazard ratio of 1.8, 1.6, or 1.4, respectively. The impact of the change to the standard of care will depend on what proportion of patients have been enrolled. If the standard of care changes before enrollment is 90% complete, we will estimate the conditional power based on the current enrollment and the expected decrease in the effect size; we would not look at the blinded study data or outcome data to estimate the conditional power. If the conditional power is < 70%, the study will be modified by increasing the sample size such that the conditional power reaches 80%. If the total required sample size to reach 80% conditional power is greater than 180, the study will be stopped for futility.

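### At the stated two-sided alpha of 0.04999, 79 events give about 86–88% power at a hazard ratio of 2.03, not 80%; the 61/41/22% quoted for smaller effects do not reproduce either

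*SAP*

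**What the plan says.** The sample-size paragraph is the same in SAP 4.2 and Protocol 12.6. It sets out the test, "Assuming 1:1 randomization and the use of a two-sided log rank test at the alpha=0.04999 level of significance for the final analysis", and then states that "79 events will provide 80% power to detect a hazard ratio of 2.03". The remaining alpha, 0.00001, goes to the interim look. With medians of 14 and 7 days, a two-month accrual, "a two-week follow-up period after randomization of the last patient, and a drop out of 10% in the control arm", the documents arrive at 120 patients (60 per arm) to obtain the 79 events.

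SAP 6 and the end of Protocol 12.6 consider a change in the standard of care. If the effect shrinks, "our expected power would decrease to 61%, 41%, or 22% under an assumed hazard ratio of 1.8, 1.6, or 1.4, respectively". The event count behind these three values is not given. A decision rule follows: "we will estimate the conditional power based on the current enrollment and the expected decrease in the effect size". Conditional power below 70% leads to a larger sample, and a required total above 180 leads to stopping for futility.

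The Protocol synopsis carries a shorter form of the claim: with 60 per arm, "we will have 80% power to detect a minimum 50% reduction in virologic shedding".

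**The concern.** Once the event count is given, the power of a log-rank test depends only on the number of events, the hazard ratio, the allocation ratio and the alpha. Accrual, follow-up and dropout decide how many patients are needed to reach 79 events; they do not change what 79 events deliver. One sentence supplies all the inputs, so the 80% can be checked directly, and it looks too low.

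The main consequence is that the published power does not follow from the published test. A reader who takes the statement at face value will understate what the trial can detect. There is also a smaller, conditional risk. The conditional-power rule calls for a fresh calculation and does not use the 61/41/22% figures. But if that calculation were run by the method that produced them, it would understate power and overstate the required sample size, tilting the decision towards enlarging or stopping the trial.

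**Working it through.** **Inputs** (SAP 4.2, Protocol 12.6): d = 79 events; 1:1 allocation; two-sided alpha 0.04999, so z = 1.960; hazard ratio (HR) 2.03. From SAP 6 and Protocol 12.6: HR 1.8, 1.6 and 1.4.

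**Formulas**

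- Schoenfeld: power = Φ(½·√d·ln HR − z)
- Freedman: power = Φ(√d·(HR − 1)/(HR + 1) − z)

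**Attempt to reproduce the 80%.** √79 = 8.888.

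- Schoenfeld: ½ × 8.888 × 0.7080 = 3.147; 3.147 − 1.960 = 1.187; Φ = 88.2%.
- Freedman: 8.888 × 1.03/3.03 = 3.021; 3.021 − 1.960 = 1.061; Φ = 85.6%.
- Simulated log-rank test (exponential times, 60 per arm, analysis at the 79th event, 20,000 runs): about 88%.

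The stated value is therefore 6 to 8 points too low. Using HR 2.0, which the medians of 14 and 7 days imply under exponential times, gives 86.9% (Schoenfeld) or 84.2% (Freedman), so rounding of the hazard ratio is not the explanation.

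**The same check in reverse.** For 80% power, z + z(0.80) = 1.960 + 0.842 = 2.802.

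- Events needed at HR 2.03: 4 × 2.802²/0.7080² = 62.6, so 63 (Schoenfeld); 2.802² × (3.03/1.03)² = 67.9, so 68 (Freedman).
- Hazard ratio detectable with 79 events: exp(2 × 2.802/8.888) = 1.88 (Schoenfeld); 1.92 (Freedman).

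**All four published powers, with 79 events**

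| HR | Stated | Schoenfeld, 0.04999 | Freedman, 0.04999 | Schoenfeld, 0.025 | Freedman, 0.025 |
|---|---|---|---|---|---|
| 2.03 | 80% | 88.2% | 85.6% | 81.7% | 78.2% |
| 1.8 | 61% | 74.3% | 71.9% | 64.5% | 61.7% |
| 1.6 | 41% | 55.1% | 53.6% | 43.9% | 42.5% |
| 1.4 | 22% | 32.1% | 31.6% | 22.8% | 22.4% |

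At 0.04999 every stated value is too low. At a two-sided alpha of 0.025 (z = 2.241) Freedman's formula comes within 2 points of all four. One wrong input, an alpha about half the stated one, would account for the whole set. This is inferred from the numbers; the documents do not say it.

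**Could a smaller event count explain the figures?** At 0.04999 the stated 80/61/41/22% would need 63/58/54/50 events (Schoenfeld) or 68/61/56/51 (Freedman). No single count gives all four, and none of these is 79.

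The secondary figures might instead assume 120 patients with fewer events as the effect shrinks. The documents do not give the ingredients, so these are assumptions: exponential times, control median 14 days, every patient followed for 14 days.

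| Dropout assumed | Events at HR 1.8/1.6/1.4 | Schoenfeld | Freedman |
|---|---|---|---|
| 10% of controls, spread over 14 days | 71.4/68.9/65.9 | 70.0/49.6/27.6% | 67.5/48.2/27.2% |
| 10% of controls contribute no events | 69.8/67.2/64.3 | 69.0/48.7/27.0% | 66.5/47.3/26.6% |
| 10% of both arms contribute no events | 65.5/63.2/60.5 | 66.2/46.3/25.8% | 63.8/45.0/25.4% |

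Every entry is above 61/41/22%. The last row comes closest, about 3 to 4 points above by Freedman, but it departs from the plan, which places dropout in the control arm only.

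**The 70% threshold.** With z + z(0.70) = 2.484, HR 1.8 reaches 70% power at 71.5 events, so 72 (Schoenfeld), or 75.6, so 76 (Freedman). Which side of the threshold it falls on therefore depends on the event count as well as on alpha.

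**The case against.** The arithmetic at 79 events is not in dispute. The strongest objections concern its weight and reach.

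- **Nothing operational changes.** The error is conservative, the sample size and type I error stand, and the conditional-power rule requires a new calculation. This is correct and limits the point to a correction of the stated figures. It does not make those figures right.
- **The synopsis sentence names no test, alpha, hazard ratio or event count.** It assumes 90% complete follow-up. If 10% of both arms contribute no events, about 68 events are expected, and power at HR 2.03 is 79.9% (Freedman) or 83.0% (Schoenfeld), so 80% can be reached there. This is fair, and the synopsis is not shown to be wrong on its own terms. It does, however, summarise the claim made in Protocol 12.6, which rests on 79 events, so it should follow whatever is restated there.
- **The fewer-events scenarios do not match the plan's premise.** The plan describes an improved standard of care, which would shorten shedding in controls. Holding treatment at a median of 7 days instead (same 14 days of follow-up, 10% of controls contributing no events) gives about 74/76/79 events and powers of 69–72/52–54/32%. This stands as a caution against treating any one scenario as the plan's implied values. It moves the powers further from 61/41/22%.
- **The primary Cox test is specified at 0.05, not 0.04999** (SAP 2.3, Protocol 12.3). That is true, but it makes no visible difference: at 0.05 the powers agree with those at 0.04999 to within 0.01 of a point.

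**Conclusion.** The concern holds. With the inputs the documents themselves state, power at a hazard ratio of 2.03 is 86–88%, so the published 80% is 6 to 8 points too low. This part needs no assumption beyond the standard log-rank approximations and is supported by simulation. The powers at 1.8, 1.6 and 1.4 are about 10 to 14 points too low if 79 events are held fixed. They are about 5 to 9 points too low if events fall with the effect and dropout is in controls only, and 3 to 4 points too low in the least unfavourable case tried. Those smaller gaps rest on the assumed exponential times and 14-day follow-up.

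A two-sided alpha of about 0.025 in the original calculation is the likely cause, but it remains an inference. The trial is better powered than it claims, and the consequence is confined to the accuracy of the power statements and to any later calculation that reuses the same method. It should be corrected.

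**What to change.** Keep 120 patients and the 0.04999 test.

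1. Confirm which alpha entered the power calculation. If it was not 0.04999 two-sided, recompute at that value.
2. In Protocol 12.6 and SAP 4.2, restate the power on a named formula. For example: with 79 events and a two-sided alpha of 0.04999, power by the Schoenfeld formula is 88% at a hazard ratio of 2.03, or 80% at 1.88.
3. In Protocol 12.6 and SAP 6, replace 61/41/22% with values recomputed at that alpha, and give the event count behind each. If 79 events are held fixed, Schoenfeld gives 74/55/32%.
4. Bring the synopsis sentence into line with the restated claim.
5. Use the confirmed alpha, with a stated event count, if the conditional-power rule is ever applied.

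The cost is a few recomputed figures and a formula name in two documents. There are no extra patients and no change to the primary test or the alpha allocation.
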